4.2.3. Sensitivity Analyses

As a sensitivity to the missing data, the following sensitivity analyses will be performed.

4.2.3.1. Tipping Point Analyses

For the tipping point analyses, the underlying response rate among those participants with missing response status in each arm will be tested ranging between 0 and 1. This analysis will be two-dimensional, *i.e.* will allow for assumptions about the assumed response rate (and thus missing outcomes) in the two arms to vary independently, furthermore they will

include scenarios where dropouts on otilimab have worse outcomes than dropouts on placebo. For combinations of the assumed response rates in the two arms, the number of additional responders among participants with missing response will be imputed multiple times by drawing from a binomial distribution. The log-odds ratio and associated standard error for each imputed dataset will be calculated using a logistic regression with treatment as the only covariate and results combined using Rubin's rules to calculate the test statistic and the corresponding p-value. Results will be presented via a heatmap.

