	
Stratification in Part 2 – Based on the study eligibility criteria, the clinical status of the participants entering Part 2 of the study will be within the two ordinal scale categories 5 and 6 and also sex, as follows:
 
• CCI [REDACTED] [REDACTED]. Male• CCI [REDACTED] [REDACTED]. Female• CCI [REDACTED] Male• [REDACTED] Female
--	--

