4.2.2. Main Analytical Approach

The primary endpoint will be summarized using counts and proportions of the number of participants alive and free of respiratory failure and will be analysed using a logistic regression model, adjusting for treatment, clinical status at baseline, sex and age as a continuous variable. The outcome of the model is an odds ratio for the treatment effect, a confidence interval and p-value for the odds of a difference in the proportion of participants alive and free of respiratory failure at Day 28, where an odds ratio >1 indicates improvement. The corresponding difference in proportion and confidence interval will be calculated [Ge, 2011].

In addition, unadjusted relative risks and risk differences will be calculated in addition to the adjusted odds ratios. These will be presented with 95% Wald confidence intervals. Any endpoint where an odds ratio/hazard ratio above 1 indicates improvement of otilimab over placebo, the inverse odds ratio/hazard ratio/relative risk will also be presented.

In addition, the following will be produced:

- A table and stacked bar chart of the proportion of participants in each category of the clinical status at each visit.
- a shift table from baseline to the clinical status at Day 4, 7, 14, 28, 42 and 60 including a row for improvement (defined as moving from a higher category to a lower category).

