4.3.3. Sensitivity Analyses

4.3.3.1. Binary Endpoints

Sensitivity analyses as per Section 4.2.3 will be performed on the binary endpoints in the hierarchy specified in Section 2.1.

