6.2. Appendix 2: Statistical Modelling

6.2.1. Multiple Imputation

Multiple imputation will be utilized to impute data that is missing following intercurrent events as detailed in the endpoint derivations.

For endpoints that are derived from the clinical status ordinal scale, as shown below, missing data will first be imputed on the ordinal scale prior to deriving the binary endpoints:

- All-cause Mortality
- Alive and Free of Respiratory Failure
- Alive and Independent of Supplementary Oxygen

For other endpoints, missing data will be imputed directly on the binary endpoint.

A monotone logistic regression imputation will be performed on both binary and ordinal endpoints adjusting for treatment and the analyses covariates.

This will be performed in a stepwise fashion, where each visit will be imputed from the selected visits preceding it, such that intermediate missing data (data that is between two non-missing values) will be imputed based only on the data that precedes it.

Death will always be considered a permanent event, such that if a subject is imputed to have died, missing data succeeding it will always be assigned the state of 'died'.

As it is expected that the data may have either a complete separation pattern or a quasi-complete separation pattern, observations will be added to each response group and then this augmented data will be used to fit a weighted logistic regression as proposed by [White \(2010\)](#)

If the logistic regression step fails to converge despite augmenting the likelihood, then a discriminant function [[Brand, 1999](#)] may be used in place of the logistic function.

A sufficient number of imputations will be performed to ensure the stability of the estimates, 10,000 imputation will be used. The results of analysis from each complete imputed dataset will be combined using Rubin's rule. [Table 4](#) details the models, covariates and the seed to be used for the analyses.

For subgroup analyses the multiple imputation model will be identical to the main endpoint analyses and the interaction term will be added into the analysis step. The chi-squared test statistic of the interaction term will be pooled using the procedure of [Rubin \(1987\)](#) and [Li \(1991\)](#).

Table 4 Multiple Imputation Specifications

Endpoint	Covariates	Post-Baseline Timepoints Included in Prediction Model	Initial Seed

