6.2.2. Tipping Point

The following seeds will be used for the tipping point analyses:

Endpoint	Initial Seed
Participants alive and free of respiratory failure at Day 28	1227
Participants alive and free of respiratory failure at Day 60	28903
All-cause mortality at Day 28	29843
All-cause mortality at Day 60	87712

The seeds were generated using the following code:

```
DATA seeds;
DO i=1 to 4;
```

```
seed=int(100000*ranuni(21409402));  
OUTPUT;  
END;  
RUN;
```

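### The Part 2 tipping-point analysis drops the primary model's covariates, so its heatmap starts from the unadjusted result and does not isolate the missing-data assumption

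*SAP*

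**What the plan says.** The primary endpoint model in Part 2 SAP section 4.2.2 is a logistic regression "adjusting for treatment, clinical status at baseline, sex and age as a continuous variable". Section 6.2.1 imputes missing outcomes under missing at random with the same kind of adjustment: "A monotone logistic regression imputation will be performed on both binary and ordinal endpoints adjusting for treatment and the analyses covariates". Clinical status and sex are also the randomisation strata (section 1.2: "within the two ordinal scale categories 5 and 6 and also sex").

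Section 4.2.3 introduces the tipping point with a single purpose: "As a sensitivity to the missing data, the following sensitivity analyses will be performed". Section 4.2.3.1 then assumes one response rate per arm for participants with missing outcomes, draws the number of extra responders from a binomial distribution, and analyses each dataset by "logistic regression with treatment as the only covariate", pooled by Rubin's rules and shown as a heatmap.

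The method is carried to other endpoints in section 4.3.3.1: "Sensitivity analyses as per Section 4.2.3 will be performed on the binary endpoints in the hierarchy specified in Section 2.1". Section 6.2.2 ("The following seeds will be used for the tipping point analyses") lists four: response at Days 28 and 60 and mortality at Days 28 and 60. It adds seeds only. No section gives a covariate-adjusted tipping point or a reason for dropping the covariates. The Part 1 SAP (section 5.2.3.1) describes the same treatment-only method.

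**The concern.** A tipping-point analysis should answer one question: how far must the missing-data assumption move before the primary conclusion changes? That requires everything except the assumption to stay fixed. Here the analysis model changes as well. A treatment-only logistic model returns the crude log odds ratio of the two-by-two table, which is a different estimate and usually a less powerful test than the one that decides the trial. The imputation also moves from a covariate-based model to one rate per arm, so no cell is built to correspond to the primary result.

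The consequence is a heatmap that can suggest that a positive result is sensitive to missing data when part of the loss of significance comes from removing covariates. This matters most when the primary p-value is near 0.05.

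**Working it through.** **Inputs from the documents.** N = 346, 1:1, 45% v 60%, about 80% power, one-sided 2.5%, minimal detectable effect 10.6 points (Protocol 8.2, SAP 5); two-sided 5% tests (SAP 2); category 6 no more than about 40% (Protocol 4.1.2.2). The documents give no covariate effects, sex split, age distribution or missing-data rate, so those below are assumptions.

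**1. The plan's own figure.** With pooled variance, n per arm = [1.960·√(2·0.525·0.475) + 0.842·√(0.45·0.55 + 0.60·0.40)]² / 0.15² = (1.384 + 0.588)² / 0.0225 ≈ 172.8, so 173 per arm and N = 346. The smallest significant difference by the pooled z-test is 10.5 points, against 10.6 stated. The design figures reproduce.

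**2. No missing data at all.** Take 104 category 5 and 69 category 6 participants per arm, with responders 62 and 16 on placebo and 74 and 22 on otilimab, that is 78/173 v 96/173.

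- Treatment only: OR = (96·95)/(77·78) = 1.52; SE of log OR = √(1/96 + 1/77 + 1/78 + 1/95) = 0.216; z = 0.418/0.216 = 1.93; p = 0.053.
- Adding baseline category: OR 1.63, z = 2.08, p = 0.038.

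The two models fall on opposite sides of 0.05 on the same complete data.

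**3. How often this happens.** 6,000 simulated trials per scenario, with permuted blocks of 4 within category by sex. Assumptions: 40% in category 6, 60% male, male OR 0.8, age 70 plus a gamma with mean 7 years, marginal rates calibrated to the stated values. Both models were fitted to the same complete data. Monte Carlo SE is 0.1 to 0.4 points.

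| Assumed OR: category 6 v 5 / per 10 years of age | Power at 45% v 60%, adjusted / treatment only | Significant only when adjusted, 45% v 60% | Same, 10.6-point difference (share of significant trials) |
|---|---|---|---|
| 0.5 / 0.7 | 0.810 / 0.789 | 2.5% | 3.9% (7%) |
| 0.3 / 0.6 | 0.837 / 0.802 | 3.9% | 5.6% (10%) |
| 0.2 / 0.5 | 0.870 / 0.819 | 5.3% | 8.5% (15%) |

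As a share of adjusted-significant trials at the design effect: 2.5/81.0 = 3.1%, 3.9/83.7 = 4.7% and 5.3/87.0 = 6.1%. With 20% in category 6 the ranges are 2.0% to 4.4% (design effect) and 2.8% to 6.1% (10.6 points). The reverse, significant only without adjustment, occurs in 0.2% to 0.9%. With no covariate effect at all, 0.8% to 0.9% are still adjusted-only, which is the background level. A second set of assumptions (unstratified randomisation; odds ratios for non-response of 2 to 8 for category 6, 1.2 to 1.5 for male sex and 1.5 to 2.0 per decade) gives 5% to 11% of adjusted-significant trials, with the reverse in 1% to 2% of all trials.

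**4. A heatmap.** Observed: 101 category 5 and 67 category 6 per arm, responders 60 and 15 on placebo and 72 and 22 on otilimab (75/168 v 94/168; category OR 0.20). Missing: 3 category 5 and 2 category 6 per arm. Rates run from 0 to 1 in steps of 0.1 in each arm (121 cells), with 2,000 imputations per cell; the adjusted version adjusts for category only.

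- Adjusted model under missing at random: p = 0.027.
- Planned treatment-only cell at the observed arm rates: p = 0.039.
- Arm-rate draws at the observed rates with the adjusted model: p = 0.028. Here the gap comes almost wholly from dropping the covariate, not from the change of imputation.
- Non-significant cells: 48 of 121 treatment only, 28 of 121 adjusted.

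With a weaker category effect (OR 0.45; 76/168 v 96/168) the counts are 30 and 28.

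**The case against.** The case for leaving it alone is substantial. Nothing confirmatory is affected: the primary estimate, its test and the type I error stand, and section 4.1.1 permits stated departures from the usual covariates. The error runs almost entirely towards apparent fragility, so the heatmap will rarely reassure falsely. Missing data should be few: Protocol 8.4.2 expects little, SAP sections 6.3.2.1 and 6.3.2.2 fill in status before last contact from ventilation, discharge and death records, and section 6.3.1 allows Days 26 to 30 for Day 28. The larger simulated figures come from a 10.6-point true difference, which sits at the significance boundary by construction. Section 4.2.2 also offers a partial anchor: "unadjusted relative risks and risk differences will be calculated in addition to the adjusted odds ratios", with Wald intervals, so a reader can see the effect of dropping covariates. Finally, a rate grid is easy to read, while a delta shift on an ordinal, visit-by-visit imputation with death as an absorbing state needs further decisions.

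These points limit the weight of the concern but do not remove it. The model mismatch exists even with nothing missing. The unadjusted intervals let a reader notice the discrepancy but do not make the heatmap test the primary conclusion, and no unadjusted odds ratio or p-value is planned to anchor it. A conservative error still misstates how robust the result is. The objection to delta shifts does not apply to keeping the rate grid and changing only the fitted model.

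**Conclusion.** The concern holds. As written, the heatmap shows how robust the treatment-only test is, not the primary test, and it is the only planned sensitivity analysis for missing data on the primary endpoint and the binary endpoints in the hierarchy. The size is modest: roughly 3% to 6% of adjusted-significant trials at the design effect are already non-significant in the treatment-only model, rising to 7% to 15% at a true difference of 10.6 points. In the worked heatmaps the excess of non-significant cells ranges from 2 to 20 of 121. All of this rests on assumed covariate strengths, and the heatmaps also on 5 missing per arm. The defect lies in what the sensitivity analysis can show; the primary analysis is sound on this point. It should be corrected because the correction is nearly free.

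**What to change.** **Smallest change.** Keep the two-dimensional rate grid. In each imputation, assign the drawn responses to individual participants with missing outcomes, fit the section 4.2.2 model (treatment, baseline clinical status, sex, continuous age), pool by Rubin's rules, and print the primary estimate and p-value beside the heatmap. Do not label any cell as missing at random, because arm-level rates only approximate that analysis.

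**Fuller change.** Apply independent arm-specific delta shifts on the logit scale to the section 6.2.1 imputation model, fit the section 4.2.2 model, and mark the cell with delta = 0 in both arms, which then corresponds to the primary result. The SAP would need to state which visits are shifted, the direction of the shift on the ordinal scale, and how it carries forward after an imputed death.

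Either change should apply to all four endpoints in section 6.2.2. The treatment-only heatmap can stay as a supplement. The cost is SAP wording and somewhat more computing, with no new data and no change to the primary analysis.

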4.2.4. Supplementary Analyses

The following supplementary analyses may be conducted.

4.2.4.1. Treatment policy estimand when correct treatment administered

Supplementary analyses to assess the impact of incorrect treatment administration may be performed using an estimand for the primary and key secondary endpoints which will analyse data as collected when the correct treatment has been administered (with a treatment policy strategy for all other ICEs). These supplementary analyses will use the same analytical approach as the main estimands and will differ only in the way that the intercurrent event of "Incorrect study treatment administered" is handled.

4.2.4.2. Composite estimand for COVID-19 medications

As a supplementary strategy to help understand the impact of some concomitant medications, a composite estimand may be considered for the handling of the intercurrent event of use of specific COVID-19 medications. A participant is considered to have an assessment of an intercurrent event if they start or increase dose of any of the known COVID-19 medications on Day 1 or later. This will be determined by a blinded review of the concomitant medications to determine whether a patient has had a new use. A participant may be considered as a non-responder if they have taken specific COVID-19 medications post-baseline. See Section 6.4.9 for a list of COVID-19 medications.

4.2.5. Subgroup Analyses

Subgroup analyses using the subgroups listed in Section 4.1.6.2 will be performed using the same methodology as the primary endpoint with the addition of a treatment by subgroup interaction. A joint test of the interaction term will be provided in the summary table. Results will be presented as per primary analyses and, in addition a forest plot of the difference in proportions will be generated.

For subgroup analyses, if there are <10 events in a subgroup then only a summary will be produced.

4.3. Secondary Endpoint(s) Analyses

The estimands are described in [Table 1](#).

4.3.1. Endpoint Definition

4.3.1.1. All-cause Mortality at Day 28 and 60

Participants will meet the endpoint if they have died due to any cause prior to Day 28 and 60. All-cause mortality will be based on the clinical status as defined in Section 6.3.2.

4.3.1.2. Time to All-cause Mortality up to Day 60

Defined as the time (days) from dosing to death, due to any cause, up to (and including) Day 60.

4.3.1.3. Participants Alive and Free of Respiratory Failure at Day 7, 14, 42, and 60

Defined as per primary endpoint, see Section 4.2.1.

4.3.1.4. Time to Recovery from Respiratory Failure up to Day 28

Defined as the time (days) from dosing to last recovery from respiratory failure up to (and including) Day 28. Participants are in respiratory failure if they are in category 5 or above from the GlaxoSmithKline (GSK) modified ordinal scale adapted from World Health Organization (WHO, 2020) scale 2020 (Table 2).

Note: if a participant has recovered from respiratory failure but then progresses back into respiratory failure on or prior to the end of follow up (Day 28) the participant has not had their last recovery from respiratory failure.

This endpoint will use a composite approach for death such that if the intercurrent event of death occurs (on or prior to Day 28), then time will be censored at end of follow up (Day 28).

4.3.1.5. Participants Alive and Independent of Supplementary Oxygen at Day 7, 14, 28, 42, and 60

Participants are independent of supplementary oxygen if they are in category 1, 2 or 3 from the GlaxoSmithKline (GSK) modified ordinal scale adapted from World Health Organization (WHO, 2020) scale 2020 (See Table 2- Ordinal Scale). Missing data prior to study withdrawal will be derived using ventilation data as described in Section 6.3.2

Participants will meet the endpoints if they are alive and independent of supplementary oxygen at Day 7, 14, 28, 42, and 60 respectively. As participants may be discharged from investigator site, analysis windows will be used to define the endpoint as described in Section 6.3.1.

4.3.1.6. Time to Last Dependence on Supplementary Oxygen up to Day 28

Defined as the time (days) from dosing to last dependence on supplementary oxygen up to (and including) Day 28. Participants are dependent on supplementary oxygen if they are in category 4 or above from the GlaxoSmithKline (GSK) modified ordinal scale adapted from World Health Organization (WHO, 2020) scale 2020 (Table 2).

Alternatively, if the clinical status is unknown but ventilation or oxygen status is available, then the endpoint is defined as the last day up to (and including) Day 28 where oxygen support is required.

Note: if a participant is independent of supplementary oxygen but then progresses back into dependence of supplementary oxygen on or prior to the end of follow up (Day 28) the participant has not had their last dependence on supplementary oxygen.

This endpoint will use a composite approach such that if the intercurrent event of death occurs (on or prior to Day 28), then time will be censored at end of follow up (Day 28).

4.3.1.7. Time to Final ICU Discharge up to Day 28

This is defined as the time (days) from dosing to the participants final ICU discharge up to (and including) Day 28. It will only be evaluated for participants in the ICU at baseline.

This endpoint will use a composite approach such that if the intercurrent event of death occurs (on or prior to Day 28), then time will be censored at the end of follow-up (Day 28), including those that were discharged from ICU prior to death.

4.3.1.8. Time to First Discharge from Investigator Site up to Day 60

This is defined as the time (days) from dosing to when the participant is first discharged from investigator site up to (and including) Day 60.

This endpoint will use a composite approach such that if the event has not occurred prior to the intercurrent event of death (on or prior to Day 60), then time will be censored at the end of follow-up (Day 60).

4.3.1.9. Time to First Discharge to Non-Hospitalized Residence up to Day 60

This is defined as the time (days) from dosing to when the participant is discharged to a non-hospitalized residence for the first time up to (and including) Day 60.

This endpoint will use a composite approach such that if the event has not occurred prior to the intercurrent event of death occurred (on or prior to Day 60), then time will be censored at the end of follow-up (Day 60).

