7.2.4. Ventilation status

Ventilation status (invasive or non-invasive ventilation), mask or nasal catheter oxygen will be collected at times outlined in the SoA (Section 1.3 and Section 1.4). For mechanically ventilated participants, indicate if the participant was in the prone or semi-prone position at any time whilst mechanically ventilated. If the participant is discharged from hospital with oxygen support, record oxygen treatment at subsequent phone call follow-ups (at times outlined in the SoA (Section 1.3 and Section 1.4).

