4.4.1.4. Alive and Not Invasively Mechanically Ventilated

Participants will meet the endpoint if they are alive and not requiring invasive mechanical ventilation at Day 7, 14, 28, 42 and 60. This will be evaluated only for participants supported using invasive mechanical ventilation at baseline. This will be derived from the worst-case ventilation record as detailed in Section 6.3.2.1.

4.4.1.5. Time to Definitive Extubation up to Day 28

For participants supported using invasive mechanical ventilation at baseline this is defined as the time from dosing (days) to final extubation from invasive mechanical ventilation up to (and including) Day 28. This will be derived from the worst-case ventilation record as detailed in Section 6.3.2.1.

This endpoint will use a composite approach for death such that if the event intercurrent event of death (on or prior to Day 28) occurs, then time will be censored at the end of follow-up (Day 28), including those that were extubated prior to death.

4.4.1.6. Oxygen-free Days up to Day 28

A participant is considered oxygen free on a day if they are not using oxygen (Ventilation=None) as derived from the worst case ventilation record on a day as detailed in Section 6.3.2.1.

Intermittent data is expected after discharge from investigator site, therefore if participants have discontinued oxygen and have been discharged to a non-hospitalized residence, they will be considered to be oxygen-free during the intermittent timepoints.

4.4.1.7. Ventilator-free Days up to Day 28

A participant is considered ventilator-free on a day if they are not using invasive mechanical ventilation as derived from the worst case ventilation record on a day as detailed in Section 6.3.2.1.

Intermittent data is expected after discharge from investigator site, therefore if participants have discontinued ventilation and have been discharged to a non-hospitalized residence, they will be considered to be ventilation-free during the intermittent timepoints.

4.4.1.8. Admission to ICU up to Day 28

Participants will meet the endpoint if they have been admitted to the ICU at any point up to (and including) Day 28, only evaluated for participants not in ICU at time of dosing.

Participants who die prior to Day 28 without being admitted ICU will be considered to have met the endpoint (composite estimands strategy).

4.4.1.9. Change from Baseline in Inspired Oxygen (FiO₂) up to Day 28

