6.3.2.2. Clinical Status Ordinal Scale

Additional derivation of clinical status will be performed. If subject dies then their clinical status will be recorded as 8-Death from date of death to Day 60 inclusive, this will override any collected clinical status.

Otherwise if clinical status is missing and the assessment day is prior to last contact with participant, then the following rules will apply:

Category	Rule
8 - DEATH	Date of death <= date of assessment
7 - HOSPITALIZED, MECHANICAL VENTILATION+ADDITIONAL ORGAN SUPPORT	Ventilation = "INVASIVE MECHANICAL VENTILATION" and additional support includes: "EXTRACORPOREAL MEMBRANE OXYGENATION" "RENAL REPLACEMENT THERAPY (RRT)/DIALYSIS" "INOTROPES/VASOPRESSORS"
6 - HOSPITALIZED, INTUBATION AND MECHANICAL VENTILATION	Ventilation = "INVASIVE MECHANICAL VENTILATION" and does not meet the classification for additional organ support

Category	Rule
5 - HOSPITALIZED, HIGH-FLOW OXYGEN(\geq 15L/MIN), CPAP, BIPAP, NIV	Ventilation is: "NON-INVASIVE MECHANICAL VENTILATION" or "HIGH-FLOW OXYGEN THERAPY (\geq 15 L/MIN)"
4 - HOSPITALIZED, LOW-FLOW OXYGEN BY MASK OR NASAL PRONGS	Ventilation = "LOW-FLOW OXYGEN THERAPY" and date of discharge to non-hospitalized residence is missing or greater than date of assessment
3 - HOSPITALIZED, NO OXYGEN THERAPY	Date of assessment < date of discharge to non-hospitalized residence and Date of assessment > date of last oxygen usage
2 - NON-HOSPITALIZED, LIMITATION OF ACTIVITY	Date of assessment > date of discharge to non-hospitalized residence and participant has not been re-hospitalized and date of assessment > date of last oxygen usage and does not meet the classification for group 1.
1 - NON-HOSPITALIZED, NO LIMITATION OF ACTIVITY	Date of assessment > date of discharge to non-hospitalized residence and participant has not been re-hospitalized and date of assessment > date of last oxygen usage and last and subsequent recorded assessment is "1 - NON-HOSPITALIZED, NO LIMITATION OF ACTIVITY".

All non-Death derived values will be flagged in the dataset.

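### In the Part 2 SAP, a discharged participant scored 1 or 2 at a follow-up call counts as independent of supplementary oxygen even when the home-oxygen record shows oxygen use that day

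*SAP*

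**What the plan says.** Two sets of secondary endpoints in the Part 2 SAP concern supplementary oxygen.

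- **Binary endpoints at Days 7, 14, 28, 42 and 60 (4.3.1.5).** "Participants are independent of supplementary oxygen if they are in category 1, 2 or 3" of the modified ordinal scale.
- **Time to last dependence up to Day 28 (4.3.1.6).** "Participants are dependent on supplementary oxygen if they are in category 4 or above". The oxygen record enters as a fallback: "Alternatively, if the clinical status is unknown but ventilation or oxygen status is available", the last day needing oxygen support is used.

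The category names appear in the derivation table of section 6.3.2.2. The two out-of-hospital categories are "1 - NON-HOSPITALIZED, NO LIMITATION OF ACTIVITY" and "2 - NON-HOSPITALIZED, LIMITATION OF ACTIVITY". Categories 4 to 7 are all labelled as hospitalized. The table's rules have limited scope. Death overrides any collected score. For everything else: "Otherwise if clinical status is missing and the assessment day is prior to last contact with participant, then the following rules will apply".

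Home oxygen is collected. Protocol section 7.2.4 says: "If the participant is discharged from hospital with oxygen support, record oxygen treatment at subsequent phone call follow-ups". The Part 2 Schedule of Activities has both the ordinal scale and home oxygen use recorded at those calls.

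**The concern.** By the printed labels, a site scoring a discharged participant who uses low-flow oxygen at home has only categories 1 and 2 to choose from, and 4.3.1.5 counts both as oxygen independence. Nothing in the plan compares that score with the oxygen use recorded at the same call. Someone sent home on oxygen and someone sent home without it then score the same on an endpoint named for not needing oxygen. If one arm discharged more people home on oxygen than the other, the treatment comparison on this endpoint would shift for a reason unrelated to oxygen need.

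**Working it through.** This is a question of definitions, and the plan states no figure to reproduce. The check applies the SAP rules literally to one participant, discharged home on Day 10 and assessed on Day 28.

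**Step 1. Binary endpoint at Day 28**

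| Situation at Day 28 | Rule | Result |
|---|---|---|
| Score collected as 1 or 2, on home oxygen | 4.3.1.5; no override except death | Independent |
| Score missing, low-flow oxygen at home | 6.3.2.2: not 1 or 2 (assessment must follow last oxygen use), not 3 (assessment must precede discharge), not 4 (discharge date must be absent or later) | No category; the value appears to go to imputation |
| Score missing, high-flow oxygen or non-invasive ventilation at home | 6.3.2.2: category 5 | Not independent |
| Score missing, no oxygen since discharge | 6.3.2.2: category 1 or 2 | Independent |

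The first two rows can be the same patient in the same state. The outcome depends on whether the site entered a score.

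**Step 2. Comparison with the rest of the SAP**

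- Derived categories 1, 2 and 3 all require the assessment to fall after the last oxygen use.
- Oxygen-free days (4.4.1.6) come from the ventilation log: "A participant is considered oxygen free on a day if they are not using oxygen (Ventilation=None" in the worst-case record for the day).
- The participant in row one therefore has no oxygen-free day on Day 28 and is oxygen-independent on Day 28.

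**Step 3. Which time points are exposed**

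The defect needs a collected post-discharge score. The schedule provides calls at Days 14, 28, 42 and 60, except that the Day 14 contact is dropped after discharge on Day 13. No Day 7 call is scheduled after early discharge, so a Day 7 status for someone already at home is normally derived, and the derivation has the oxygen condition.

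**Step 4. Time to last dependence**

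Let the same participant use low-flow oxygen continuously through Day 28, with a 2 collected on Days 14 and 28. Days 11 to 13 and 15 to 27 have no score and fit no derived category, so the fallback in 4.3.1.6 uses the oxygen record and shows dependence. On Day 28 the collected 2 says no dependence. Last dependence falls on about Day 27 and counts as an event. On the oxygen record, dependence had not ended by Day 28 and the participant would be censored.

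**Step 5. Size, on assumed inputs only**

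The documents give no home-oxygen rate. There are 346 / 2 = 173 participants per arm. Assume 35–45% are at home at Day 28 with a collected 1 or 2, and 10–30% of those use oxygen:

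- low end: 173 × 0.35 × 0.10 = 6.1 participants (3.5 percentage points);
- high end: 173 × 0.45 × 0.30 = 23.4 participants (13.5 percentage points).

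For the treatment difference, borrow 45% and 60% from the primary-endpoint sample size as apparent independence rates. Let h_P and h_O be the shares of those counted independent who use home oxygen on placebo and otilimab. The corrected difference is 0.60(1 − h_O) − 0.45(1 − h_P).

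| h_P | h_O | Corrected difference |
|---|---|---|
| 0% | 0% | 0.600 − 0.450 = 15.0 points |
| 5% | 5% | 0.570 − 0.4275 = 14.25 points |
| 10% | 10% | 0.540 − 0.405 = 13.5 points |
| 20% | 20% | 0.480 − 0.360 = 12.0 points |
| 5% | 15% | 0.510 − 0.4275 = 8.25 points |
| 15% | 5% | 0.570 − 0.3825 = 18.75 points |

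Equal shares shrink the difference modestly. Larger shifts, in either direction, need unequal shares.

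**The case against.** The strongest objection is that the full scale in Table 2 is redacted. Its wording, the eCRF guidance or the study reference manual may tell sites how to score home oxygen. The printed labels do not settle it: the derived rule for category 5 has no hospitalization condition despite its label, and the oxygen condition on derived categories 1 and 2 suggests that the sponsor may read them as oxygen-free. This stands as a limit on confidence. It does not supply the missing cross-check, and if the sponsor does read categories 1 and 2 that way, collected scores should meet the same condition.

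The impact is also limited. These endpoints are outside the hierarchy in section 2.1. The primary endpoint accepts categories 1 to 4, so low-flow home oxygen does not change it. All of that stands.

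A reader might infer more than the documents support:

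- **Every participant on home oxygen is counted as independent.** No. With a missing score, the derivation does not make them independent.
- **All five time points are affected alike.** No. Day 7 is largely unaffected.
- **The last-dependence event falls at discharge.** No. Status is unscored between calls, and the oxygen record then governs.
- **A drug effect on home oxygen could not be seen.** No. Section 4.4.1.10 summarizes oxygen use after discharge, and oxygen-free days are modelled from the log.
- **The treatment comparison is biased.** The documents give no evidence that home-oxygen use differs between arms.

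**Conclusion.** The point holds for collected scores. At the Day 14, 28, 42 and 60 calls, a recorded 1 or 2 is taken as oxygen independence whatever the home-oxygen record says, and at Day 28 the same score can turn a participant still on oxygen into an event for time to last dependence. The SAP treats the same state differently when the score is derived and when it counts oxygen-free days, so this is an internal inconsistency as well as a measurement problem. The conclusion rests on the section 6.3.2.2 labels reflecting how sites score. The size is unknown: the 6 to 23 participants per arm and the shifted differences above are illustrations on assumed rates. It should be corrected because the plan already holds the data to do so, but it does not threaten the primary conclusion or the hierarchical tests.

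**What to change.** 1. In 4.3.1.5, require clinical status 1, 2 or 3 **and** Ventilation = None on that day from the section 6.3.2.1 log.
2. In 4.3.1.6, define dependence as clinical status 4 or above **or** any oxygen on the log, whether or not a status was recorded.
3. Apply the log condition before multiple imputation, so that low-flow home oxygen with a missing status, which fits no derived category, is set to not independent.
4. If the unredacted scale or site guidance already covers home oxygen, say so in the SAP.

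The cost is SAP wording and one added condition in each derivation. No new data are needed, since ventilation status is already derived for Days 1 to 60. Reported independence rates will be somewhat lower. The main risk is in the log: section 6.3.2.1 treats entries without an end date as ongoing, so an unclosed entry would create false dependence. Those entries must be queried before database freeze.
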